1.4.2. Significance Level and Confidence Interval of the Test

The significance level of the test is set at a two-tailed 5%, and the confidence level of the confidence interval is set at a two-tailed 95%.

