1.4.5.2. Linear Mixed Effects Model

run ;

Note: [pre-post treatment group variable] and [case number variable] are categorical values, [time (year) variable] is a continuous value.

The INT in the random statement is specified as is, meaning the intercept. The intercept and slope vary between individuals.random.

2. Statistical Analysis

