2.4. Aggregation Regarding Efficacy

2.4.1. Rate of Change in Bilateral Total Kidney volume

[Analysis Target]

Cases subject to efficacy analysis

Cases with one measurement date at baseline and before baseline are classified as the pre-administration group, and cases with one or more measurement dates during administration are classified as the post-administration group.

An analysis will be conducted on cases that fall into either the pre-administration group or the post-administration group.

[Analysis Method]

Regarding the rate of kidney volume increase

1) To reduce heterogeneity of variance and achieve linearity over time, the data of bilateral total kidney volume is log-transformed (log10). This log-transformed bilateral total kidney volume is set as the dependent variable, and a linear mixed-effects model is fitted as repeated measures data. The explanatory variables of the model are the administration group, time (years), patient, interaction of administration group and time, and interaction of patient and time as fixed effects, and the intercept and slope of the time axis for each patient as random effects. The variance-covariance matrix of the random effects is unstructured. The annual change rate and 95% confidence interval are returned to

their original scale by (10 estimated value -1) x 100.

Time (years) is calculated as "(measurement date - baseline +1) \div 365.25".

- 2) The pre-administration group calculates the rate of kidney volume change from before the baseline to the baseline, and the post-administration group calculates the rate of kidney volume change from the baseline to after the baseline. The rate of change in kidney volume is calculated using the following formula.
 - Rate of kidney volume change = {((post-administration value pre-administration value) / pre-administration value) x 100} / "period (years) from the start of administration of this drug to the measurement date"

Also, the Estimated Slope and Estimated SE are calculated for each of the pre-administration group and the post-administration group, and a graph is created. The difference in the Estimated Slope between the pre-administration group and the post-administration group and its test result are displayed as the estimated value of the parameter based on the solution of the fixed effect of the administration group and time and the p-value based on the t-distribution.

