2.4.2. Change in e-GFR

[Analysis Target]

Cases subject to efficacy analysis

Cases with one measurement date at baseline and before baseline are classified as the pre-administration group, and cases with one or more measurement dates during administration are classified as the post-administration group.

Analyses targeting cases that apply to either the pre-administration group or the post-administration group (however, excluding cases that only have two points: one at baseline and one either before baseline or during administration) will be conducted.

[Analysis Method]

- 1) e-GFR will be treated as the dependent variable using actual values, and a linear mixed-effects model will be applied as repeated measurement data. The explanatory variables of the model are the administration group, time (years), patient, interaction of administration group and time, and interaction of patient and time as fixed effects, and the intercept and slope of the straight line over time for each patient as random effects. The variance-covariance matrix of the random effects will be unstructured.
- 2) The change in e-GFR from before baseline to baseline for the pre-administration group, and the change in e-GFR from baseline to after baseline for the post-administration group will be calculated. The change in e-GFR will be calculated using the following formulas:
 - Pre-administration change = (Pre-baseline value Baseline)
 - Post-administration change = (Post-administration value Baseline)

In addition, the Estimated Slope and Estimated SE will be calculated separately for the preadministration group and the post-administration group. The difference in the Estimated Slope between the pre-administration group and the post-administration group and its test result will be displayed as the estimated parameter values based on the solution of the fixed effects of the administration group and time, and the p-value based on the t-distribution.

Reference

- 1. Marc Froissart, Jerome Rossert, Christian Jacquot, Michel Paillard and Pascal Houillier: Predictive performance of the modification of diet in renal disease and Cockcroft-Gault equations for estimating renal function. J Am Soc Nephrol 16: 763-73, 2005.

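### The mixed models give each patient one slope across both periods, so if the slope change at drug start varies between patients, the model-based standard error of the pre/post slope difference is too small

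*SAP*

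**What the plan says.** SAP 2.4.1 models log10 total kidney volume and SAP 2.4.2 models e-GFR with the same structure. Besides group and time, the fixed effects are "patient, interaction of administration group and time, and interaction of patient and time as fixed effects". The random part for kidney volume is "the intercept and slope of the time axis for each patient as random effects", and for e-GFR "the intercept and slope of the straight line over time for each patient as random effects". On their covariance, 2.4.1 states "The variance-covariance matrix of the random effects is unstructured"; that setting covers only the intercept and slope. The note that survives under 1.4.5.2 agrees: "The intercept and slope vary between individuals".

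The reported comparison is the pre/post slope difference. In 2.4.1, "The difference in the Estimated Slope between the pre-administration group and the post-administration group and its test result are displayed", taken from "the solution of the fixed effect of the administration group and time and the p-value based on the t-distribution". I read this as the group x time coefficient. Section 2.4.2 does the same for e-GFR, and 1.4.2 sets a two-sided 5% level and 95% intervals. The method text describes no robust standard error and no sensitivity analysis.

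**The concern.** Administration group varies within a patient. SAP 1.2 excludes from the efficacy set cases with no measurement after administration, so patients who supply pre-baseline data will generally supply on-drug data too. For them, a patient-specific slope shared by both periods largely drops out of the pre/post contrast. The contrast's uncertainty should then include how much the slope change itself differs between patients. Neither model has a term for this: there is no random group x time and no patient x group x time. The model-based variance is therefore right only if every patient's slope changes by the same amount at drug start. The SAP neither states nor justifies that, although it accepts that slopes differ between patients.

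These slope differences are the only efficacy results for which the SAP specifies a test. An understated standard error makes the intervals too narrow and a change in progression too easy to declare. Enrolling more patients does not help, because the ratio of the model-based to the true standard error does not depend on their number.

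**Working it through.** The documents give no variance component, visit schedule, power or standard error for this comparison, so there is no planned figure to reproduce. Structure and test level come from SAP 2.4.1, 2.4.2 and 1.4.2; everything numerical below is an assumption.

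**Model and truth.** Planned: y = β0 + β1·g + β2·t + β3·g·t + b0 + b1·t + e, with g = 0 up to and including baseline, g = 1 on drug, and b0, b1 per patient. Truth used for the check: the same plus d·g·t, where d is the patient's own deviation from the average slope change, with mean 0 and SD σd. The true β3 is zero.

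**Why longer history matters (rough guide).** With one scan T years before baseline, the noise variance of a patient's own pre-slope is 2σ²/T². With residual SD σ = 0.015:
- T = 1: 2 × 0.000225 / 1 = 0.00045
- T = 3: 2 × 0.000225 / 9 = 0.00005

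The omitted variance σd² is 0.000036 (σd = 0.006) or 0.000144 (σd = 0.012). That is 8% or 32% of the pre-slope noise at 1 year, and 72% or 288% at 3 years.

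**Large-sample check.** Step 1: find the planned model's variance parameters that minimise log|V| + tr(V⁻¹Σ), where Σ is the true covariance including d. Step 2: r = model-based SE of β3 / true (sandwich) SE of β3. Step 3: true rejection rate = 2Φ(−1.96 r).

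Assumptions: 1 to 5 years on drug in equal shares, all patients with data in both periods, baseline entered once, d independent of b0 and b1.
- Kidney volume (log10): between-patient slope SD 0.012/yr, residual SD 0.015, one earlier scan, annual scans on drug.
- E-GFR (mL/min/1.73m²): slope SD 2.5/yr, residual SD 4, quarterly values on drug. SAP 2.4.2 does not make clear whether one or several pre-baseline values enter, so both are shown.

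| Outcome, pre-baseline data | σd | r | True rejection |
|---|---|---|---|
| Kidney volume, 1 yr | 0.006 / 0.012 | 0.972 / 0.908 | 5.7% / 7.5% |
| Kidney volume, 3 yr | 0.006 / 0.012 | 0.882 / 0.722 | 8.4% / 15.7% |
| e-GFR, one value, 1 yr | 1.25 / 2.5 | 0.978 / 0.921 | 5.5% / 7.1% |
| e-GFR, one value, 2 yr | 1.25 / 2.5 | 0.924 / 0.778 | 7.0% / 12.8% |
| e-GFR, one value, 3 yr | 1.25 / 2.5 | 0.862 / 0.663 | 9.1% / 19.4% |
| e-GFR, quarterly, 1 yr | 1.25 / 2.5 | 0.972 / 0.903 | 5.7% / 7.7% |
| e-GFR, quarterly, 2 yr | 1.25 / 2.5 | 0.876 / 0.681 | 8.6% / 18.2% |
| e-GFR, quarterly, 3 yr | 1.25 / 2.5 | 0.768 / 0.527 | 13.2% / 30.2% |

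Rates use unrounded r; two entries lie near a rounding boundary (12.75% and 30.15%). With σd = 0, r = 1.000 and the rate is 5.0% in every design.

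**Partial absorption.** In the kidney volume case with a 3-year-old scan and σd = 0.012, the fitted residual SD rises from 0.015 to 0.0175. Some of the variation is picked up, but not enough.

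**Fixed patient x time.** Fitting the patient terms as fixed gives 8.0% and 14.6% for the 3-year kidney volume case, close to 8.4% and 15.7%. Settling fixed versus random does not cure the problem.

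**Does the sandwich estimator work?** Simulation, 300 patients, 600 runs, kidney volume, 3-year-old scan:
- σd = 0.006: model-based rejection 7.3%, sandwich 4.8%.
- σd = 0: model-based 4.5%, sandwich 4.8%.

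Monte Carlo error near 5% is about √(0.05 × 0.95 / 600) = 0.9 points.

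**The case against.** **The code cannot be seen.** Under 1.4.5.2 only a closing run statement and a note survive in the extracted text. A reader might infer that the code has no robust option or patient-within-period subject; missing text cannot show that. What stands is that both method sections and the note describe effects per patient, and no prose mentions a robust standard error.

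**The standard error may be correct.** A reader might infer that the p-value is certainly too low, or that the model ignores the variation altogether. Neither is supported. With a common slope change the test holds at 5.0%, and part of any variation goes into the residual and random-effect variances.

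**The large values need strong assumptions.** Fair. With one pre-baseline measurement 1 year back, no scenario above exceeds 7.5%. The upper figures need long history and a slope-change SD as large as the whole between-patient slope SD. Large e-GFR figures based on quarterly history should not be quoted as the SAP's design.

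**Not all patients are paired.** Section 2.4.1 admits cases in either group. This changes little. In a separate e-GFR grid (4 quarterly values before, 12 after, with residual, slope and slope-change SDs numerically equal), r was 0.814 with all patients paired and 0.813 with 30% paired.

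**Baseline may enter twice.** The row layout is unspecified. If baseline is used in both groups, the planned kidney volume test rejects at 10.0% to 11.8% even with no slope-change variation. That is a separate fault and is excluded from the figures above.

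**No confirmatory claim is planned.** This is a single-arm survey with no stated primary hypothesis, power or success criterion, so a reader should not infer that a formal success claim turns on this test. A p-value at a stated 5% level will still be reported and should be valid.

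**Conclusion.** The point holds conditionally. As described, both models leave out between-patient variation in the slope change; wherever it exists, the standard error of group x time is too small and its p-value too low. Under the assumed variances the effect is minor with a single measurement 1 year before baseline. It becomes material with 2 to 3 years of history, more so if many pre-baseline e-GFR values are used. The direction is well founded when slope changes vary; the size cannot be settled from the documents. It merits a change to the SAP but does not show that the survey's result will be wrong.

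**What to change.** In 2.4.1, 2.4.2 and the code of 1.4.5.2, state that standard errors, confidence intervals and p-values for the slopes and for group x time come from the patient-clustered sandwich estimator (EMPIRICAL option, subject = case number), and that this is the reported result. State the degrees-of-freedom method. If the full code already has the option, only the prose needs the sentence.

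Add a patient-level random group x time term only as a sensitivity analysis where it converges. One pre-baseline scan plus baseline supports it weakly: in simulations with 400 patients and 250 runs its rejection rate was 3.2% to 8.0%, with Monte Carlo error of about 1.4 points, against 6.4% to 30.8% for the planned model.

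The cost is one code option and one sentence per section. The downside is a wider confidence interval when slope changes vary; when they do not, the simulation showed almost no loss.

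### The SAP does not say how the shared baseline record enters the pre/post mixed model; if it is entered once per period, the standard error of the tested slope difference is too small

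*SAP*

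**What the plan says.** For kidney volume, SAP 2.4.1 states: "Cases with one measurement date at baseline and before baseline are classified as the pre-administration group". By contrast, "cases with one or more measurement dates during administration are classified as the post-administration group"; baseline is not named there.

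Step 1 of the method fits a linear mixed model to log10 volume. It has group and time terms, then "patient, interaction of administration group and time, and interaction of patient and time as fixed effects", plus a random intercept and slope per patient with unstructured covariance. The tested quantity is the difference between the pre and post slopes, with a t-based p-value. Step 1 does not say under which group level the baseline row is entered.

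Step 2, the per-case rate of change, does place baseline. It is the last point of the pre period. It is also the first point of the post period, where the text reads: "the post-administration group calculates the rate of kidney volume change from the baseline to after the baseline".

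SAP 2.4.2 repeats this structure for e-GFR. Its analysis target also drops cases with only two points, described as "one at baseline and one either before baseline or during administration". Section 2.4.1 has no such exclusion.

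On coding, the note in SAP 1.4.5.2 says that "pre-post treatment group variable] and [case number variable] are categorical values" and that time is continuous. The model code itself is not in the text available for review; that is not held against the plan. SAP 1.4.2 adds: "The significance level of the test is set at a two-tailed 5" percent.

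**The concern.** Three places treat baseline as belonging to both periods: the definition of the pre group, the two step 2 periods, and the e-GFR exclusion. In addition, a single on-treatment scan qualifies a patient for the post group, and that scan gives a within-patient post slope only if baseline is also a post-group point. With a categorical period variable, a patient in both groups then needs the baseline record in the data set twice.

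The two copies are one reading with one error. A baseline that reads high makes the pre slope steeper and the post slope flatter, so the two estimated slopes are negatively correlated and their difference is more variable than the model believes. Nothing in the described model lets two rows share a residual. The duplicated rows also agree perfectly with each other, which pulls the estimated residual variance down.

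The result would be a confidence interval that is too narrow and a p-value that is too small for the only efficacy test described in 2.4.1 and 2.4.2. This happens with no drug effect and no patient selection, so it is separate from regression to the mean.

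**Working it through.** The SAP gives no standard error, residual SD, interval to the earlier scan or number of scans per patient, so there is no stated figure to reproduce.

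**Inputs from the documents:** two-sided 5% (SAP 1.4.2); model terms and periods (SAP 2.4.1); categorical period (SAP 1.4.5.2); up to 8 years of survey (protocol, survey period).

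**Assumptions:** baseline row duplicated; independent residuals with variance σ²; one earlier scan d years before baseline; k annual on-treatment scans; same schedule for everyone; no variation between patients in slope change.

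**Step 1: slope variances.** The pre slope uses times −d and 0. The post slope is least squares on 0, 1, …, k with weights w, where w₀ is the baseline weight.
- Treating the two baselines as independent: V₀ = σ²(2/d² + Σw²).
- True value, with one shared baseline error: V = V₀ − 2σ²w₀/d. Since w₀ is negative, V exceeds V₀.

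For d = 1, k = 1: V₀ = 2 + 2 = 4σ². Directly, the difference is y₁ − 2y₀ + y₋₁, so V = 1 + 4 + 1 = 6σ². The ratio √(4/6) = 0.816 is an 18.4% understatement.

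**Step 2: residual variance.** Once each patient has an intercept and slope, the duplicated pair lowers the estimated residual variance to f·σ², with f = 1 − 2h/(n − 2) and h = 1/n + t̄²/Sₜₜ. Here n, t̄ and Sₜₜ are the number, mean and centred sum of squares of the row times. For d = 1, k = 1 the times are −1, 0, 0, 1, so h = 1/4 and f = 1 − 0.5/2 = 0.75. The model reports 0.75 × 4 = 3σ² against a true 6σ². The ratio is √(3/6) = 0.707, a 29.3% understatement.

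**Step 3: more on-treatment scans.** Type I error is 2[1 − Φ(1.96 × ratio)]. With d = 1:

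| k | V₀/σ² | V/σ² | f | SE ratio √(fV₀/V) | Understatement | Type I error |
|---|---|---|---|---|---|---|
| 1 | 4 | 6 | 0.750 | 0.707 | 29.3% | 16.6% |
| 3 | 2.2 | 2.8 | 0.885 | 0.834 | 16.6% | 10.2% |
| 7 | 2.024 | 2.190 | 0.948 | 0.936 | 6.4% | 6.7% |

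The large-sample limit of the planned mixed model gives the same understatements. They did not change with patient effects fixed or random, residual SD 0.01 to 0.04, or slope SD 0.01 to 0.02 (log10).

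**Step 4: longer gap.** With d = 2 the understatement is 27.5%, 20.5% and 9.3% for k = 1, 3 and 7. With d = 3 the SE ratios are 0.75, 0.79 and 0.88.

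**Step 5: not everyone in both groups.** Patients in one group have no duplicated row. If 20% to 80% have a pre-baseline value (d = 1), the understatement is 20.5% to 27.8% for k = 1, 11.2% to 15.6% for k = 3, and 4.4% to 6.0% for k = 7. At 4.4% the type I error is about 6%.

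**Step 6: e-GFR.** With assumed quarterly values the SE ratio is 0.931 to 0.944, giving 6.4% to 6.8%.

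**Step 7: each measurement entered once.** With terms time and max(time, 0), the SE ratio is 1.00 and the type I error 5.0% in every schedule tried.

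**The case against.** The strongest objection is that double entry is inferred. The sentences that put baseline on both sides describe the step 2 rate calculation, not the model, and step 1 is silent on row coding. Independent residuals are likewise the usual default rather than something the visible text states. A programmer who coded rows by date could place baseline once, in the pre level, because the post group is defined by dates during administration. The understatement is then 0.0% for 2, 3, 4 and 7 on-treatment scans when patients do not differ in slope change. If they do differ (assumed SD 0.01 log10 per year), 1.2% to 4.6% remains, but duplication does not cause it.

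This stands as a limit on certainty, but it does not settle the matter. With baseline only in the pre level, a patient with one on-treatment scan has no within-patient post slope, although 2.4.1 admits such patients. With baseline only in the post level, a patient with one earlier scan has no within-patient pre slope. The SAP needs to say what is done.

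A reader might also infer that the SAP definitely enters the record twice and that the standard error is 16% to 20% too small. The documents support neither. That band fits only some schedules, such as about three annual on-treatment scans, and the plan states no schedule.

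Finally, this is a survey with no stated decision rule, and the e-GFR effect is small under quarterly values. Both are fair and limit the consequence. The test and interval will still be reported at nominal levels.

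**Conclusion.** The point holds conditionally. The SAP uses baseline as the end of one period and the start of the next, codes period as categorical, and leaves the row structure unstated. If the record is entered under both levels with independent residuals, the standard error of the tested slope difference was too small in every schedule tried.

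For kidney volume the understatement is about 4% to 29%, a true type I error of about 6% to 17%. It is largest with few on-treatment scans, and smaller with many scans or few patients in both groups. The range rests on assumed annual scans, a gap of 1 to 3 years to the earlier scan, and no variation in slope change. For e-GFR the effect is small on the quarterly schedule assumed; it too depends on how many values each patient has.

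**What to change.** In SAP 2.4.1 and 2.4.2, state that each measurement enters the model once. Replace the group and group-by-time terms with time from drug start and max(time, 0), and test the coefficient of the second term as the slope change. Patients with values on one side only can stay in.

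An on-drug step term can be added to keep the level shift that the planned group effect allows; without it, any immediate shift is absorbed into the slope change. A patient with one on-treatment scan cannot separate step from slope, so the SAP should say whether the step is in the main model or a sensitivity analysis. Patient-clustered sandwich standard errors are optional.

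The cost is SAP wording and program code, with no new data. The reported confidence interval becomes somewhat wider, most where scans are few: with one scan a year either side of baseline, the standard error goes from √3σ to √6σ per patient, a factor of 1.41.

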Study ID: I15600-003

Samsca drug use-results survey (ADPKD) Study Protocol

NCT Number: NCT02847624

Otsuka Pharmaceutical Co., Ltd.

Protocol Creation Date: February 21, 2014, Version 1.0 Date of the latest version: September 2, 2021, Version 8.0

Objective of	To determine the safety and efficacy of Samsca used in routine clinical settings for suppression of
survey	ADPKD progression.
Survey	<all patients="" survey=""></all>
methods	All patients treated with Samsca must be registered in the survey until "CONDITIONS FOR
	APPROVAL" is removed.
	CRFs must be collected from all patients until the total number of patients registered in the survey
	reaches the planned number.
	Observation period: From start of Samsca administration through the end of survey
	In case of finish or discontinue of Samsca administration, collecting information of kidney
	volume, changes in renal function and hepatic dysfunction (outcome: not recovered) through
	the end of survey (8 years).
Survey period	8 years (March 24,2014 ~ March 23,2022)
Planned	1,600
number of	Depending on the onset of significant drug-induced liver injury post-marketing, the planned
patients to be	number of patients will be re-evaluated and necessity of additional safety measures will be also
surveyed	assessed.
	In addition, if there is a substantial change in expected number of patients with long-term
	treatment (≥4 years), the planned number of patients will be re-evaluated so as to collect at least
	800 patients with long-term treatment.
Target patient	All patients treated with Samsca after March 24, 2014 for the indication of "suppression of
population of	ADPKD progression with a rapid kidney volume increase in patients with increased kidney
• •	volume"
Major items to	1
	CRFs of drug use-results survey (for treatment period) 1) Patient information
be surveyed	
	Patient initials (last name, first name), patient ID, sex, any breast feeding, any pregnancy,
	date of birth (age), date of informed consent received (in written form)
	2) Patient demographics
	Indication for use, time of ADPKD diagnosis, diagnosis of ADPKD (severity of ADPKD,
	family history, number of cysts, complications (especially, hepatic cyst, pancreatic cyst,
	cerebral aneurysm, urinary calculus, any complication of cyst infection), past history,
	predisposition to hypersensitivity, history of drug adverse reactions
	3) Administration status of Samsca

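### SAP 2.4.1 item 2) annualises kidney-volume change by simple division, so the individual rate depends on interval length and does not match the compound annual rate of item 1)

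*SAP*

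**What the plan says.** SAP 2.4.1, Analysis Method, has two numbered items.

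- **Item 1)** fits a linear mixed-effects model to transformed volume: "To reduce heterogeneity of variance and achieve linearity over time, the data of bilateral total kidney volume is log-transformed (log10". The annual change rate and its confidence limits are then put back on "their original scale by (10 estimated value -1) x 100". The exponent is flattened in the extracted text; the meaning is (10^estimate - 1) x 100, a compound percentage per year.
- **Item 2)** defines an individual rate for each group and introduces it with "The rate of change in kidney volume is calculated using the following formula". The pre-administration interval ends at baseline. For the interval on drug, "the post-administration group calculates the rate of kidney volume change from the baseline to after the baseline". In the formula, the change is divided by the starting value, multiplied by 100, then divided by the "period (years) from the start of administration of this drug to the measurement date". It has no log step and no compounding.

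On interval length, the section says only how the groups are formed. For the time before the drug: "Cases with one measurement date at baseline and before baseline are classified as the pre-administration group". For scans on drug, the rule is that "cases with one or more measurement dates during administration are classified as the post-administration group". The section neither limits nor matches the intervals. The Protocol gives the survey period as "8 years (March 24,2014 ~ March 23,2022" and aims for at least 800 patients treated for 4 years or more.

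**The concern.** The two items yield annual percentage rates for the same quantity, but they annualise differently. Item 1) assumes a constant proportional increase each year. Item 2) spreads the total percentage increase evenly over the years. Under compound growth these agree only when the interval is one year.

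Two patients with identical growth but different follow-up would therefore receive different item 2) rates. If pre-drug intervals tend to be shorter than on-drug ones, a summary of item 2) rates by group would show faster growth on drug where none exists, or would understate a real slowing. Kidney-volume change is one of only two efficacy items in the Protocol's list of items to be analysed. A reader comparing the two rates could not separate the formula's effect from the drug's.

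This is distinct from the date at which the item 2) divisor starts. Measuring time correctly between the two scans would still leave the dependence on length.

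**Working it through.** The plan states no growth rate and no worked example, so there is no figure of its own to reproduce.

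**Inputs**
- Growth model, from SAP 2.4.1 item 1): log10 volume linear in time, so V(t) = V0 x (1+g)^t.
- Individual rate, from SAP 2.4.1 item 2): percentage change from the starting value, divided by years. Here t is taken as the time between the two scans, to isolate the functional form.
- Longest possible on-drug interval, from the Protocol: 8 years.
- True annual growth g: not in the documents. Assumed at 3%, 6% and 10%.
- Pre-drug interval: not in the documents. Assumed at 1 year for the pre/post illustration.

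**Step 1. Item 2) rate under item 1)'s model**

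R(t) = 100 x ((1+g)^t - 1) / t

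Because (1+g)^t is convex in t, R(t) rises with t for any non-zero g. For example, at g = 6% and t = 5: 1.06^5 = 1.3382, and 33.82 / 5 = 6.76.

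| Assumed g | 1 year | 3 years | 5 years | 8 years |
|---|---|---|---|---|
| 3% | 3.00 | 3.09 | 3.19 | 3.33 |
| 6% | 6.00 | 6.37 | 6.76 | 7.42 |
| 10% | 10.00 | 11.03 | 12.21 | 14.29 |

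The spurious excess of an 8-year over a 1-year interval is 0.33 points at 3%, 1.42 at 6% and 4.29 at 10%.

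**Step 2. A real slowing, 6% before the drug (1-year interval) and 5.5% on drug**

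The pre rate reads 6.00. The on-drug rate, 100 x (1.055^t - 1) / t, reads:
- 3 years: 5.81
- 4 years: 5.97
- 5 years: 6.14
- 8 years: 6.68

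The slowing is nearly erased at 4 years and changes sign by 5 years.

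**Step 3. Measurement error**

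With an assumed log-scale (natural log) error SD of s = 0.05 per scan, g = 5% and no between-patient slope variation, the expected rate is 100 x (exp(t x ln 1.05 + s^2) - 1) / t:
- 0.25 years: 5.92
- 0.5 years: 5.45
- 1 year: 5.26
- 2 years: 5.26
- 4 years: 5.46
- 8 years: 6.01

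Error inflates the rate at very short intervals, so the rise with length need not hold below about 1 year. It is present again beyond about 2 years.

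**Step 4. Compound form**

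100 x (((1+g)^t)^(1/t) - 1) = 100 x g at every t. Without scan error, the dependence on length disappears and the rate is on item 1)'s scale.

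**The case against.** **Nothing inferential rests on item 2).** The pre/post slope difference and its p-value come from the mixed model's fixed effects, and the back-transformed annual rate with its interval comes from the same model. This stands. A reader might infer that the planned test is biased; the SAP does not support that.

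**The graph is probably not affected.** A reader might also infer that the graph is distorted. The graph sentence is tied to the estimated slopes and their standard errors, so it most naturally shows model output. The SAP specifies no table of item 2) rates either. This stands.

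**Simple annualisation is a legitimate description.** Average yearly change as a percentage of the starting value is a coherent quantity, and the log transform is justified for modelling. That is fair for a single fixed interval. It does not help when intervals vary and the result is set beside a compound rate for the same outcome.

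**Unequal intervals are assumed.** Pre-drug interval lengths are not given, and 8 years is a ceiling rather than a typical interval. The SAP's exclusion rule in 1.2 mentions permitted windows at evaluation times, so rates might be reported by visit with the duration visible. All of this stands and makes the pre/post bias conditional. Variation in length within the on-drug group is harder to dismiss, given the target of at least 800 patients treated for 4 years or more.

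**The pre-group formula is already incomplete.** Its divisor counts from the start of administration, so the pre-drug rate has to be rewritten anyway. That is true, and compounding belongs in the same edit.

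**Conclusion.** The inconsistency within SAP 2.4.1 is real. Under the section's own growth assumption, individual item 2) rates from intervals of different length are not comparable with each other or with item 1)'s annual rate.

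The size depends on assumed growth and interval. Between 1 and 3 years the excess is 0.09 points at 3% per year and 0.37 at 6%; between 1 and 8 years it is 0.33 and 1.42. Any bias in the descriptive pre/post comparison requires unequal intervals. If on-drug intervals are the longer ones, as the 8-year survey and the long-term treatment target make plausible, the bias runs against the drug. With equal intervals there is no spurious pre/post difference, and scan error may offset the effect below about 1 year.

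It would go too far to say that the formula will reverse a true slowing. In the 6% to 5.5% example a reversal needs 5 to 8 years on drug against 1 year before; at 4 years the rate reads 5.97, still below 6.00. The point concerns descriptive rates. It should be corrected, but it does not undermine the model-based efficacy result.

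**What to change.** In SAP 2.4.1 item 2), define the individual rate for both groups as

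{(later value / earlier value)^(1 / years between the two measurement dates) - 1} x 100,

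equivalently (10^[(log10 later - log10 earlier) / years] - 1) x 100. This matches the back-transformation in item 1).

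Writing it with later and earlier values, and with time between the two scans, also settles how the formula applies to the pre-administration group. Reporting the distribution of interval lengths by group beside the rates would let a reader judge how far the intervals differ.

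The cost is one formula in the SAP and one line of code. No new data are needed, and the mixed model does not change.
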